14.4 COMMUNICATION PROCEDURES

During the course of the study, all correspondence (letters, telephone call, emails and faxes) regarding the study must be maintained in the study binder provided by the Study Sponsor. This binder must be made available for monitoring visits or audits.

15 DATA MONITORING COMMITTEE

The Study Sponsor with an independent Data Monitoring Committee (DMC) will monitor all serious adverse events. The DMC will consist of a minimum of 3 members, all members being physicians; one cardiothoracic surgeon, one interventional cardiologist and one cardiologist.

[REDACTED]

[REDACTED]

16 STUDY STOPPING RULES

[REDACTED]

- [REDACTED]
- [REDACTED]
- [REDACTED]
- [REDACTED]
- [REDACTED]
- [REDACTED]

[REDACTED]

17 ETHICAL AND REGULATORY CONSIDERATIONS

17.1 APPLICABLE REGULATIONS AND GUIDELINES

The regulations listed in Table 11 must be observed to comply with the Study Sponsor policy for conduct and of clinical studies; they also represent sound research practice. It is the responsibilities of the Investigator(s) to comply with the requirements set forth in their country specific regulations.

Table 11 - Applicable Regulations and Guidelines

Region	Regulation / Guideline
United States	
 - 93/42/EEC European Medical Device Directive (MDD) - EN ISO 13485:2012 Medical Devices - Quality Management Systems - Requirements for Regulatory Purposes - ISO 14155:2011 (E) (Clinical Investigation of Medical Devices for Human Subjects) - ISO 14971:2012 (Application of risk management to medical devices)

Furthermore, the Investigator(s) must comply with the requirements of the Declaration of Helsinki (2008) and with of ICH E6 GCP or with laws of the foreign country, whichever will afford greater protection to the subject screened for participation in the clinical study and subjects who participate in the study.

17.2 DATA PROTECTION AND SUBJECT CONFIDENTIALITY

The Study sponsor is dedicated to maintaining the confidentiality and privacy of subjects who volunteer to participate in the study. Passwords are issued to appropriate personnel to insure confidentiality and protection of the database by allowing variable levels of access to the computer system. In addition, the Principal Investigator is responsible for maintaining confidentiality throughout the clinical study. The hard copies of the source documentation are to be maintained in a secure area with limited access. All subject identifiers will be obliterated from all photocopies of source documents that have been removed from the study site. Subject identifiers include, but are not limited to: subject's name, social security number or equivalent, and medical / hospital number. All study documents for the clinical study will identify the subject by a subject study identification number assigned by the Sponsor and the subject's initials (if applicable).

17.3 INVESTIGATOR RESPONSIBILITIES

17.3.1 GENERAL DUTIES

The Investigator shall ensure that all work and services described herein, or incidental to those described herein, shall be conducted in accordance with the highest standards of

medical and clinical research practice and the applicable regulations. The Investigator shall be responsible for the day to day conduct of the clinical study and for the safety and well-being of subjects enrolled. The Investigator will provide copies of the current study protocol to all staff responsible for study conduct.

The Investigator is responsible for obtaining and maintaining EC approval for the study at his/her study center.

If there is a change or addition of an Investigator, an amended Clinical Study Agreement must be completed promptly.

17.3.2 INVESTIGATOR RECORDS

The Investigator will maintain the accurate, complete, and current records relating to participation in this clinical study. Study records including CRFs and supporting data, signed Clinical Study Agreement, protocols and protocol amendments, signed informed consents, device tracking logs, EC approval letters, EC submissions, correspondence, including required reports, and other documents pertaining to the conduct of the study must be kept on file by the Investigator. If the Investigator wishes to assign the responsibility of maintaining the study files to someone else or move them to another location, he/she should consult with the Study Sponsor in writing regarding the change. Upon Study completion, the study files must be maintained in a known location for a period in accordance with local regulatory requirements.

17.3.3 INVESTIGATOR REPORTS

[Redacted]

- | [Redacted]
- | [Redacted]
- | [Redacted]
- | [Redacted]
- | [Redacted]
- | [Redacted]
- | [Redacted]
- | [Redacted]
- | [Redacted]
- | [Redacted]
- | [Redacted]

17.4 SPONSOR RESPONSIBILITIES

17.4.1 GENERAL DUTIES

As the Study Sponsor of this clinical study, Edwards Lifesciences has the overall responsibility for the conduct of the study, including assurance that the study meets the regulatory requirements of the pertinent regulatory agencies.

In addition, the Study Sponsor declares that no employee/affiliate of the Sponsor or Investigator will be included or encouraged to participate in this investigational study.

The Study Sponsor will inform the Investigator of any new information about the study that may affect the health, safety or welfare of the subjects or which may influence patient's decision to continue participating in the study.

Additionally, interruptions in the study or recruitment due to significant amendments will also be reported to the applicable regulatory authorities.

17.5 SELECTION OF INVESTIGATORS

17.5.1 MONITORING THE STUDY

The Study Sponsor will ensure compliance with the signed clinical agreement, the protocol (investigational plan), the requirements of applicable regulations and guidelines (see section 17.1) and any conditions of study approval by the EC and regulatory bodies. Edwards will conduct an immediate investigation of any unanticipated adverse device effects (UADE) and if an event is found to present an unreasonable risk to study subjects, the Study Sponsor will inform Investigators, ECs, and regulatory bodies as required.

17.5.2 SPONSOR RECORDS

The Study Sponsor will maintain accurate, complete, and current records relating to this clinical study. Study records include CRFs, signed Clinical Study Agreement, signed financial disclosure, protocols and protocol amendments, informed consent, device use, EC approval letters, submissions, correspondence, including required reports, and other documents. The Study Sponsor will maintain study documentation during the study and for a period in accordance with local regulatory requirements after the study is terminated or completed, or the study records are no longer required to support a regulatory submission. Storage of the study records may be designated to a third party.

17.5.3 SPONSOR REPORTS

[Redacted]

- [Redacted]
- [Redacted]
- [Redacted]
- [Redacted]
- [Redacted]
- [Redacted]
- [Redacted]
- [Redacted]
- [Redacted]

17.6 STUDY CHANGES

Changes in the protocol may be made only by written amendment agreed upon by the Study Sponsor, the regulatory agency and EC. As appropriate, the Study Sponsor will submit protocol amendments to the pertinent regulatory agencies and Investigators to obtain EC approval prior to implementation.

17.7 STUDY COMPLETION OR TERMINATION AND CLOSE-OUT

The Investigator will be notified in writing upon termination/conclusion of the study. Edwards Lifesciences retains the right to suspend or terminate this clinical study at any time.

Safety and review committees associated with the study may recommend termination should safety concerns warrant such action as described in Section 16.

All study subjects enrolled up to the point of study termination, will continue to be followed as per protocol requirements.

17.8 AUDITS AND INSPECTIONS

In the event that audits are initiated by the Study Sponsor or national/international regulatory authorities, the Investigator shall allow access to the original medical records and provide all requested information, as applicable.

17.9 PUBLICATION POLICY

[REDACTED]

19 DEFINITIONS

Access Site	Access site defined as any location (venous) traversed by a guidewire, a catheter or a sheath (including the subclavian or axillary vein)
ACT	Activated clotting time
Acute Kidney Injury (AKI)	Refer to VARC-2 definition
Adverse Device Effect (ADE)	Refer to ISO 14155 definition
Adverse Event (AE)	Refer to ISO 14155 definition

Adverse Event Causality
	
Not related: Relationship to the device or procedures can be excluded when:
 
 • The event is not a known side effect of the product category the device belongs to or of similar devices and procedures • The event has no temporal relationship with the use of the investigational device or the procedures • The serious event does not follow a known response pattern to the medical device (if the response pattern is previously known) and is biologically implausible • The discontinuation of medical device application or the reduction of the level of activation/exposure - when clinically feasible – and reintroduction of its use (or increase of the level of activation/exposure), do not impact on the serious event • The event involves a body-site or an organ not expected to be affected by the device or procedure • The serious event can be attributed to another cause (e.g. an underlying or concurrent illness/ clinical condition, an effect of another device, drug, treatment or other risk factors) • Harms to the subject are not clearly due to use error • In order to establish the non-relatedness, not all the criteria listed above might be met at the same time, depending on the type of device/procedures and the serious event 
Unlikely: The relationship with the use of the device seems not relevant and/or the event can be reasonably explained by another cause, but additional information may be obtained.
 
Possible: The relationship with the use of the investigational device is weak but cannot be ruled out completely. Alternative causes are also possible (e.g. an underlying or concurrent illness/ clinical condition or/and an effect of another device, drug or treatment). Cases where relatedness cannot be assessed or no information has been obtained should also be classified as possible.
 
Probable: The relationship with the use of the investigational device seems relevant and/or the event cannot reasonably be

---------------------------------------	--

	
explained by another cause, but additional information may be obtained.
 
Causal Relationship: The serious event is associated with the investigational device or with procedures beyond reasonable doubt when:
 
 • The event is a known side effect of the product category the device belongs to or of similar devices and procedures • The event has a temporal relationship with investigational device use/application or procedures • The event involves a body-site or organ that the investigational device or procedures are applied to or have an effect on • The serious event follows a known response pattern to the medical device (if the response pattern is previously known) • The discontinuation of medical device application (or reduction of the level of activation/exposure) and reintroduction of its use (or increase of the level of activation/exposure), impact on the serious event (when clinically feasible) • Other possible causes (e.g. an underlying or concurrent illness/ clinical condition or/and an effect of another device, drug or treatment) have been adequately ruled out • Harm to the subject is due to error in use • In order to establish the relatedness, not all the criteria listed above might be met at the same time, depending on the type of device/procedures and the serious event
--	---

Cardiac Tamponade
	
Pressure on the heart that occurs when blood or fluid builds up in the space between the heart muscle (myocardium) and the outer covering sac of the heart (pericardium).

Cardiovascular Mortality
	
Refer to VARC-2 definition

Cerebrovascular Accident (CVA)
	
See "Stroke"

Clinical Outcomes	
Clinical Outcomes (at 1 month, 6 months & Annually)
 
 • Re-hospitalization rates for the underlying condition (heart failure) • Re-intervention rates for the underlying condition (tricuspid regurgitation) • Change in Tricuspid Regurgitation (assessment made by change in EROA) from baseline • Change in peripheral edema as assessed by subject weight loss (kilograms) from baseline • Change in NYHA Class from baseline • Change in 6 minute walk test distance (meters) from baseline • Change in Quality of Life as assessed by the SF-12 and KCCQ questionnaires from baseline
Death	All cause mortality
Device Deficiency	Refer to ISO 14155 definition
Device Detachment	Separation, under the action of applied stress or strain, of any part of the investigational device that was previously intact.
Device Embolization	Refer to ISO 5840-3 definition
Device Malfunction	Refer to ISO 14155 definition
Device Migration	Refer to ISO 5840-3 definition
Device Success	
Device Success (at 1 month, 6-months and annually):
 
 • Alive, with • Original intended device in place, and • No additional surgical or interventional procedures related to the device, and • TR reduction (assessment made by change in EROA) compared to baseline and TV gradient $\leq 5\text{mmHg}$
Embolism	
Free flowing blood clot or lesion material that is located in the systemic or pulmonary circulation.
 
A peripheral embolic event is an operative, autopsy or clinically documented embolus that produces symptoms from complete or partial obstruction or a peripheral (noncerebral) artery.

Emergency Surgery
	
Emergent Salvage: The patient is undergoing CPR en route to the operating room or prior to anesthesia induction
 
Emergent: All of the following conditions are met:
 
 • Not elective status • Not emergent salvage status • Procedure required before procedure room exit in order to minimize chance of further clinical deterioration • Any surgical procedure on the previously implanted study device (repair, alteration or replacement) or study procedure access site post-implant procedure 
Elective: The patient’s cardiac function has been stable in the days or weeks prior to the operation. The procedure can be deferred without increased risk of compromised cardiac outcome.

Endocarditis
	
An inflammation of the inside lining of the heart chambers and heart valves (endocardium). Endocarditis can involve the heart muscle, heart valves, or lining of the heart.

Enrollment
	
Subject enrollment in this clinical study is established when a subject has signed the informed consent form agreeing to participate in the study and has been deemed eligible for study participation by meeting the study criteria.

Explant
	
Removal of the study device after completion of the implant procedure for any reason.


Heart Failure
	
Heart Failure - A progressive condition that involves loss of pumping ability by the heart (heart muscle weakens and gradually loses its ability to pump enough blood through the body), generally accompanied by fluid accumulation in body tissues, especially the lungs.
 
Heart Failure Hospitalization - An unplanned hospitalization that results in at least one overnight stay (i.e., where the admission date and the discharge date are different) that includes increased signs and/or symptoms of worsening heart failure and requires the administration or augmentation of existing heart failure therapy.
 
Severe Heart Failure – See NYHA Class IV

HEART Team
	
The ‘HEART Team’, for the purpose of this study, must include a minimum of one Cardiologist, and one Cardiac Surgeon.

Hemolysis (Device Hemolysis)	
Rupturing of red blood cells (erythrocytes) and the release of their contents (cytoplasm) into surrounding fluids.
 
Device hemolysis is defined as hemolysis in or near the investigational device that interferes with the function of the device. Device hemolysis related thrombus may be confirmed by operation, autopsy, or diagnostically by such methods as echocardiography, angiography, or magnetic resonance imaging.

Implant procedure	Placement of the investigational device in the tricuspid valve regurgitant orifice.
Infection	Known infection requiring intravenous antibiotics for other than prophylaxis, and/or extended hospitalization.
INR	International normalized ratio
IVC	Inferior vena cava
KCCQ	Kansas City Cardiomyopathy Questionnaire is a health-related quality-of-life measure for patients with congestive heart failure.
LVEF	Left ventricular ejection fraction
Malfunction	Refer to ISO 14155 definition
Myocardial Infarction	Refer to VARC-2 definition
New York Heart Association Classification (NYHA Class)	
Class I: Patients with cardiac disease but without resulting limitations of physical activity.
 
Class II: Patients with cardiac disease resulting in slight limitation of physical activity. Patients are comfortable at rest. Ordinary physical activity results in fatigue, palpitation, dyspnea, or anginal pain.
 
Class III: Patients with cardiac disease resulting in marked limitation of physical activity. They are comfortable at rest. Less than ordinary physical activity causes fatigue, palpitation dyspnea, or anginal pain.
 
Class IV: Patients with cardiac disease resulting in inability to carry on any physical activity without discomfort. Symptoms of cardiac insufficiency or of the anginal syndrome may be present even at rest. If any physical activity is undertaken, discomfort is increased.

Nonstructural Dysfunction	Abnormality extrinsic to the repair device that results in valve dysfunction (stenosis, regurgitation or both)
Patient	A person with the disease (tricuspid regurgitation) being screened to participate in the clinical study.

Peripheral Thromboembolic Event	See “Embolism”
Pre-Existing Condition	A pre-existing condition is one that is present at the start of study treatment.
Primary Endpoint	The primary endpoint for the study will assess the all-cause mortality of the as treated cohort at 30 days compared to a literature derived Performance Goal based on high-risk surgical outcomes for tricuspid repair/replacement.
Procedural Success	Procedural Success (at 1 month): 
 • Device Success, and • None of the following device or procedure related SAEs: 
 • Life threatening bleeding • Major vascular or cardiac structural complications requiring intervention • Pericardial effusion requiring drainage or surgery (includes tamponade) • Stage 2 or 3 acute kidney injury (includes new dialysis). • Severe heart failure or hypotension requiring IV inotrope, ultrafiltration or mechanical circulatory support • Prolonged intubation > 48 hours
Prosthesis	An artificial substitute
QoL	Quality of Life
Reintervention	Any intervention on the previously implanted study device (repair, alteration or replacement) or study procedure access site post-implant procedure.
Renal Failure	See “Acute Kidney Injury (AKI)”
Screen Failure	A patient who has signed the consent but, does not meet the inclusion criteria or who meets at least one of the exclusion criteria.
Serious Adverse Device Effect (SADE)	Refer to ISO 14155 definition
Serious Adverse Event (SAE)	Refer to ISO 14155 definition
SF-12	A short survey with 12 questions that results in two scales of mental and physical functioning and overall health related quality of life.
Six (6) MWT	Six minute walk test
Stroke/TIA	Refer to VARC-2 definition
Subject	Refer to ISO 14155 definition

Subject Withdrawal	A subject who decides not to participate in the study after signing an informed consent form and being enrolled.
Technical Success	
Technical Success (at exit from procedure room):
 
 • Alive, with • Successful access, delivery and removal of the delivery systems, and • Deployment and correct positioning of the intended device, and • No need for additional emergency surgery or re-intervention related to the device or access procedure
Thromboembolic Event	See “embolism”
Thrombus (Device Thrombosis)	
An aggregation of platelet, fibrin, clotting factors, and other cellular elements exclusive of infection.
 
Device thrombosis is defined as any thrombus in the absence of infection attached to or near the investigational device that interferes with function of the device. An investigational device related thrombus may be confirmed by operation, autopsy, or diagnostically by such methods as echocardiography, angiography, or magnetic resonance imaging.

Tricuspid Regurgitation	Tricuspid Regurgitation (TR), tricuspid insufficiency or tricuspid incompetence describes a condition in which blood flow through the tricuspid valve flows in the incorrect direction during part of the cardiac cycle.
Unanticipated Serious Adverse Device Effect (USADE)	Refer to ISO 14155 definition
Valvular Leak (See Also “Nonstructural Dysfunction”)	Any evidence of leakage of blood through the native valve leaflets and around the investigational device. Diagnosis of valvular leak may be obtained from echo; however definitive diagnosis is obtained at reoperation, explant, or autopsy.
Withdrawal by Investigator	A subject who consents to participate in the study and is enrolled but is withdrawn by the Investigator.

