- deterioration of native valve (leaflet tear/tearing, leaflet retraction, leaflet thickening, leaflet stenosis, or other);
- device degeneration;
- device explants;
- device migration, malposition or embolization potentially requiring intervention;
- device thrombosis requiring intervention;
- emergency cardiac surgery;
- hemolysis;
- leakage around device;
- non-emergent reoperation;
- nonstructural implant dysfunction;
- papillary muscle damage;
- pneumothorax;
- pulmonary artery outflow tract obstruction;
- skin burn;
- structural deterioration (wear, fracture, calcification, shaft creep, or other);
- thromboembolism (permanent or transient pulmonary and/or neurological events);
- transvalvular flow disturbances;
- valvular regurgitation;
- ventricular or atrial wall damage, abrasion, or perforation;
- worsening of heart failure;
- worsening of valvular insufficiency.

There may be other risks that are unknown at this time. All safety events will be collected and reviewed throughout the entire study and follow-up period. The Investigators will be notified of any additional risks identified that could affect the health, safety or welfare of the study subjects.

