5.2.1 TECHNICAL SUCCESS ENDPOINT

Technical Success will be assessed at exit from procedure room and is defined as:

- Alive, with
- Successful access, delivery and removal of the delivery systems, and
- Deployment and correct positioning of the intended device, and
- No need for additional emergency surgery or re-intervention related to the device or access procedure

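### The Section 19 definition of Emergent surgery is narrower than the Technical Success endpoint it serves, so a surgically repaired cardiac wall injury could be scored as a success

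*Protocol*

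**What the plan says.** Technical Success is assessed at exit from the procedure room in the As Treated cohort (Protocol 5.2.1 and 13.3; SAP 2.3.2, 2.4 and 4.3.1). Besides survival, access, delivery, removal and deployment, it requires "No need for additional emergency surgery or re-intervention related to the device or access procedure".

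The SAP repeats this endpoint but does not define emergency surgery, so Protocol Section 19 governs. The Emergency Surgery entry there has three categories: Emergent Salvage, Emergent and Elective.

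- Emergent Salvage has a single test: "The patient is undergoing CPR en route to the operating room or prior to anesthesia induction".
- The Emergent category opens with "All of the following conditions are met", and four bullets follow. The first is that the surgery is not elective. The second is "Not emergent salvage status". The third is "Procedure required before procedure room exit in order to minimize chance of further clinical deterioration". The fourth is "Any surgical procedure on the previously implanted study device (repair, alteration or replacement) or study procedure access site post-implant procedure".

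Two other Section 19 entries bear on this. Access Site is any venous location passed through by a guidewire, catheter or sheath. Reintervention is limited in nearly the same words as the fourth Emergent bullet: the implanted device or the access site, after implant.

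**The concern.** The endpoint and the definition draw different boundaries. The endpoint turns on whether the operation was related to the device or the access. The definition turns on whether the operation was performed on the device or the access site. An operation on the heart wall for an injury that the device caused satisfies the first test and fails the second.

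This is not a remote scenario for this device. Protocol 3.1 lists "ventricular or atrial wall damage, abrasion, or perforation" among the additional risks of using the FORMA System, and the same list includes emergency heart surgery.

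At stake is the classification of a serious procedural complication in a secondary performance endpoint, in a study whose data are meant to support regulatory approval (Protocol Section 2). Under the literal text the error runs in the device's favour. Two people scoring the same case could also reach different answers, depending on which section they apply.

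**Working it through.** The plan states no figure for this point, so there is none to reproduce. The check is one of logic, followed by the size of a single misclassified case.

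**Rule as written.** Emergency surgery = Emergent Salvage, OR (not elective AND not salvage AND needed before room exit AND on the implanted device or access site, post-implant).

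**Cases put through the rule and the rest of Technical Success:**

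| Case | Emergency surgery? | Reintervention? | Technical Success |
|---|---|---|---|
| Atrial or ventricular wall perforation, repaired before room exit, no CPR; alive, device correctly placed, delivery system removed | No (fourth condition fails) | No (not device or access site) | **Success** |
| Perforation of a traversed vein, repaired before room exit, after implant | Yes (the vein is an access site) | Not needed | Failure |
| Wall perforation with CPR on the way to the operating room | Yes (Emergent Salvage has no site condition) | Not needed | Failure |
| Perforation before implantation, device never placed | No | No | Failure, on the deployment component |
| Death before room exit, or failed access, delivery or removal | Not needed | Not needed | Failure, on those components |

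Only the first row is misclassified. The heart chambers do not help, because the Access Site entry names venous locations only. The Reintervention entry does not help either, because it stops at the same boundary.

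**Size of one case.** Scoring one subject as a success instead of a failure moves the rate by 1/N. Inputs from Protocol 13.1: 63 subjects planned for analysis, 78 enrolled, up to 9 roll-ins.

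- N = 63: 1/63 = 0.0159, or 1.6 points.
- N = 78 − 9 = 69 (roll-ins removed, no dropout before room exit): 1/69 = 0.0145, or about 1.4 points.
- N = 78: 1/78 = 0.0128, or 1.3 points.

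The visible text gives no perforation rate, so the expected number of such cases cannot be computed.

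**The case against.** A reader might infer more than the text supports. The tempting reading is that any emergency operation for a device-caused perforation escapes Technical Success, or that the most serious procedural complications go uncounted. The table shows otherwise. Repair of a traversed vein after implant counts, salvage cases count, and death counts. An operation before implantation may miss the Emergent label, but a subject who never receives the device fails on deployment. Nor is the room-exit condition a flaw: Technical Success is itself assessed at room exit, so the two match.

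Four further arguments deserve weight.

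- The endpoint's own wording lets an adjudicator count a repaired perforation, and its qualifier would be nearly redundant if emergency surgery already meant only surgery on the device or access site. This stands. The fault is an inconsistency between the definition and the endpoint, not a settled exclusion.
- The fourth bullet is a noun phrase, not a condition, and nearly duplicates the Reintervention entry. It may have been misplaced, or its list level lost in text extraction. This is possible but cannot be confirmed from the text available.
- "Successful access, delivery and removal of the delivery systems, and" might be read to fail such a case on its own. But the text does not say that an injury during an otherwise completed delivery makes the delivery unsuccessful.
- The event is visible elsewhere. As a device- or procedure-related SAE it would normally fail Procedural Success, either as a structural complication needing intervention or as a pericardial effusion needing drainage or surgery. It would also appear in the adverse event listings and be reviewed by the sponsor and the DMC. This limits the harm. It does not correct Technical Success, which is a separate endpoint with a different time point and cohort.

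**Conclusion.** The point holds in a narrow form. On the literal text, a cardiac wall or other cardiac structural injury, surgically repaired before room exit without CPR, in a living subject with the device correctly placed and the delivery system removed, would be scored a Technical Success. That conflicts with the endpoint's own wording.

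Each such case would raise the Technical Success rate by about 1.3 to 1.6 points, depending on whether the denominator is nearer 78 or 63. No total effect can be stated, because the documents give no expected number of cases.

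The conclusion assumes that the four bullets are joint conditions, as the lead-in says, and that Section 19 governs the endpoint's terms. The 30-day mortality endpoint is not touched. The documents attach no hypothesis, performance goal or power to Technical Success. This is a low-priority wording correction, worth making because a stated rule, applied as written, misclassifies in the device's favour.

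**What to change.** In the Emergency Surgery entry of Protocol Section 19, keep the first three Emergent conditions. Replace the fourth with: and the surgery is related to the study device, delivery system or access procedure, including surgery on the device, surgery on the access site, or surgery for cardiac or vascular injury that any of these caused.

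Section 19 then matches the endpoint in Protocol 5.2.1 and SAP 2.3.2 and 4.3.1, whose wording can stay. The Reintervention entry need not change for this purpose, since the operation in question would be caught as emergency surgery.

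The cost is one reworded definition, with no new data, visits or subjects. The downside is that Technical Success may be slightly lower.
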